10/Sessions 19 & 20	Problem solving: Part 5	Review and continued practice of cognitive control and problem-solving skills across multiple contexts/situations.

3.B. Procedure. Patients will be recruited through an ongoing VA Merit Study (PI: [name]) at the JJPVAMC, “*Neurobiology of affective instability in Veterans at Low and High Risk for Suicide*” that already has in place recruitment and assessment procedures for diagnosis. To date, the PI has recruited and screened >200 Veterans for this Merit study and ~100 of them met the stringent study criteria and received structured clinical interviews and MRI scans. The proposed study leverages support from the parent study for recruitment, as the Veterans have already been screened and diagnosed. See **Human Subjects** and **Appendix 2**.

3.C. Participants. Inclusion criteria. Age 18-60; U.S. Veteran; primary diagnosis of MDD and history of suicide attempt in the past year; elevated score (>1SD above the normal mean) on rumination measure (Ruminative Response Scale;⁴³ see **Table 3.D**, below); based on the Columbia-Suicide Severity Rating Scale (C-SSRS)⁴⁴:

current suicidal ideation (either passive, i.e. “wish to be dead”) or active ideation but with no intent to act on it immediately and no specific plan; and currently in psychotherapy treatment as usual (TAU) at the JJPVAMC. We will include women and aim for the sample to be 30% women. *Exclusion criteria.* Current substance use disorder; history of traumatic brain injury; neurological disorder, or other medical confound; compromised intellectual abilities (WASI⁴⁵ FSIQ<70). *We will enroll six Veterans in each group and conduct six 10-week intervention cycles for a total sample of 36 Veterans. See Appendix 3 for Enrollment Table.*

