3.F. Timeline. As shown in **Table 3.F**, the CR+Bridging open trial will be conducted with six groups (each group including six Veterans for the 10-week intervention) during months 4-16 with Week 10/Post-tx and Week 20/Follow-up sessions conducted during months 8-21. Data collection will be completed in month 21, followed by data analysis. Manuscript writing and CSR&D Merit Award RCT application submission will occur during months 23-24. A potential limitation that may impact the success of this project is recruitment of Veterans during this challenging time of COVID-19. However, a strength of the proposed clinical intervention study is that it involves telehealth, making it more appealing to participants and less prone to high no-show rates.

Table 3.F. Study Timeline.	Year:	1	1	1	1	1	1	1	1	1	1	1	1	2	2	2	2	2	2	2	
	Month:	1	2	3	4	5	6	7	8	9	10	11	12	13	14	15	16	17	18	19	20
Train staff/Obtain IRB approval:		x	x	x																	
Conduct open trial: Group #				1	1	1	2	2	3	3	3	4	4	5	5	5	5	5	5	5	
Note: Each group includes 6																					
Veterans/patients: 6 groups x 6 = 36 (total)																					
Conduct baseline/pre-tx assessments:			x		x			x		x			x								
Week 10/post-tx & 20/follow-up assessments:								x	x	x	x	x	x	x	x	x	x	x	x	x	
Data entry/analysis:				x	x	x	x	x	x	x	x	x	x	x	x	x	x	x	x	x	
Submit papers and RCT VA Merit Award																		x	x	x	
																		x	x	x	

3.G. Statistical Approach. Rationale for Proposed Sample Size (which applies to all aims): We used data from a similar CR study in civilians⁵³ to determine our sample size. Hamilton Depression Rating Scale (self-report measure that includes the same symptoms as the clinician-administered MADRS¹³ which we will use in the proposed study) scores from pre- and post-CR intervention from Naismith et al⁵³ were used to provide estimates of change in depression severity that we can apply to the MADRS. Using a sample size of 22 achieves 90% power to detect a mean of paired differences of 3.2 with an estimated standard deviation of 4.35 for differences and with a significance level of 0.05 using a two-sided paired t-test. For the current pilot study, we will enroll 36 Veterans in the intervention and we conservatively anticipate up to 40% attrition. This means that even with only 22 completers, we will still be well-powered for the proposed analyses.

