Aim 1: Sample size: Definitive conclusions about the efficacy of the CR+Bridging intervention cannot be made based on this pilot study's findings. We plan to use the data collected to: (1) calculate power for a larger confirmatory study and (2) examine acceptability and feasibility data. We plan to submit a VA Merit application that will involve a rigorous RCT to determine efficacy of this novel intervention.

Analysis: We will calculate descriptive statistics, e.g., means, standard deviations, minimum, maximum for continuous measures (e.g., CR+Bridging treatment fidelity ratings, retention), as well as count and frequencies for categorical measures (e.g., attendance). We will be able to compare these descriptive statistics to published rates of recruitment, engagement, and attendance of similar type interventions.

Aim 2: Sample Size: Using a two-sided paired t-test to compare MADRS¹³ before and after for each subject, for 90% power at a 5% level of significance and assuming a decrease in MADRS with a range of standard deviations from 1 to 10, we can detect a mean paired difference of -0.7 to -6.5 for 22 Veterans.

Analysis: MADRS¹³ and Iowa Gambling Task (IGT^{11, 12}) scores are the primary outcome variables here. For all of the study completers, each outcome measure will be compared initially between Baseline and Week 10 (pre- vs. post-intervention) by paired t-test. As a secondary analysis, all outcome measures in Table 3.D will be compared this way as well. Correction for multiple comparisons will be performed using a Holm's correction.

For exploratory analyses, outcome variables that reach significance for Pre-tx/Baseline vs. Post-tx/Week 10 comparisons will also be analyzed across all three time points (Baseline, Week 10, Week 20/Follow-up) using a linear mixed-effects model with unstructured correlation between time points.

Missing data will be assumed to be missing at random and handled accordingly by multiple imputation. All statistical tests will be 2-tailed with alpha=0.05.

Aim 3: Sample Size: This aim is exploratory. We will utilize the same sample size as shown in the sample size section and acknowledge that we may be underpowered for these analyses.

Analysis: Each outcome measure (e.g., QACPOA¹⁵, LIFE-RIFT¹⁶) will be compared initially between Baseline and Week 10 by a paired t-test and if either show significance, then they will be compared across all three time points using the same mixed-effects model analysis as described in Aim 2.

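### Treatment is delivered in six therapy groups, but the Aim 2 paired t-test and its 90% power count Veterans as independent; if changes correlate within groups, the standard error is too small.

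*Combined protocol and SAP*

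**What the plan says.** All references are to the combined protocol and SAP.

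- **Delivery.** Section 3.C: "We will enroll six Veterans in each group and conduct six 10-week intervention cycles for a total sample of 36 Veterans". Section 3.A describes a manualised group programme in which computer exercises are followed by a shared Bridging discussion. Section 3.D has one clinical neuropsychologist deliver all 20 sessions of each cycle.
- **Sample size.** Section 3.G: "Using a sample size of 22 achieves 90% power to detect a mean of paired differences of 3.2", with an SD of differences of 4.35 and a two-sided 5% test. Of the 36 enrolled, "we conservatively anticipate up to 40% attrition", which leaves about 22.
- **Primary Aim 2 analysis.** MADRS and Iowa Gambling Task (IGT) are primary. For study completers, "each outcome measure will be compared initially between Baseline and Week 10 (pre- vs. post-intervention) by paired t-test".
- **Exploratory model.** Outcomes that reach significance are then analysed at all three visits "using a linear mixed-effects model with unstructured correlation between time points".
- **Multiplicity and missing data.** "Correction for multiple comparisons will be performed using a Holm's correction". "Missing data will be assumed to be missing at random and handled accordingly by multiple imputation".
- **Status.** Under Aim 1: "Definitive conclusions about the efficacy of the CR+Bridging intervention cannot be made" from this pilot. The data will also be used to calculate power for a larger study.

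Section 3.G mentions no therapy-group term, ICC, design effect or cluster-robust standard error. It also does not say that independence is assumed.

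**The concern.** Veterans in one cycle share twenty sessions, the same peers and the same calendar period during the pandemic. Sections 1 and 1.C present peer support as part of what the group format is meant to provide, so some similarity of change within a group, especially in mood, is plausible. There is no control arm, so anything that shifts a whole cycle goes straight into the mean change.

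The paired t-test handles the dependence between a Veteran's own two measurements. It does not handle dependence between Veterans in the same group. If that is positive, the estimated mean change stays unbiased, but its standard error is too small, the interval too narrow and the test too liberal. At stake are the confidence intervals for mean MADRS and IGT change, the choice of outcomes that go forward to the three-visit model (which depends on significance), and the claim to be well powered with 22 completers.

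**Working it through.** **Inputs.** From section 3.G: n = 22 completers, mean change 3.2, SD of change 4.35, two-sided alpha 0.05. From 3.C: six groups of six. Assumptions: ICC of change 0, 0.05, 0.10 or 0.20 (the documents give none); 22 completers spread 4, 4, 4, 4, 3, 3; 4.35 taken as the total SD of change.

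**1. The plan's own figure.** Planned SE = 4.35/√22 = 0.93. Noncentrality = 3.2/0.927 = 3.45. The noncentral t with 21 df gives 90.8% power. The stated 90% therefore reproduces with independent changes.

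**2. Standard error under clustering.** Design effect = 1 + (m − 1) × ICC, with m = Σmᵢ²/n = (4×16 + 2×9)/22 = 82/22 = 3.73. At ICC 0.05 this is 1 + 2.73 × 0.05 = 1.14, so the true SE is √1.136 = 1.07 times the planned one. The effective sample size is 22/1.136 = 19.4.

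**3. Effect on the planned analysis.** Coverage, type I error and rejection rates come from simulation (normal changes with a shared group component, 400,000 trials per setting). A separate run of 300,000 per setting agreed to within simulation error. Power with a corrected SE is the noncentral t (21 df) with the SE multiplied by the square root of the design effect.

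| Assumed ICC | 0 | 0.05 | 0.10 | 0.20 |
|---|---|---|---|---|
| Design effect | 1.00 | 1.14 | 1.27 | 1.55 |
| True SE (MADRS points) | 0.93 | 0.99 | 1.05 | 1.15 |
| True / planned SE | 1.00 | 1.07 | 1.13 | 1.24 |
| Coverage of nominal 95% CI | 95% | 93.5% | 92% | 88.5% |
| Real size of the 5% test | 5% | 6.5% | 8% | 11.5% |
| Planned test rejects at 3.2 points | 91% | 90% | 88% | 87% |
| Power with corrected SE | 91% | 87% | 83% | 75% |

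The planned test's rejection rate at 3.2 points hardly moves, because the understated SE offsets the lost information. The cost appears in coverage and type I error, or in power once the SE is corrected.

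**4. If all 36 complete.** Now m = 6, and the 5% test runs at about 5% / 8% / 11% / 17%. Better retention enlarges the inflation, because more Veterans share each group.

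**5. Holm.** The plan does not define the Holm family. If it is MADRS and IGT, both null, uncorrelated and with the same ICC, the family-wise error is about 4.9% / 6.9% / 8.9% / 13.5%. If IGT has ICC 0 while MADRS has 0.05 / 0.10 / 0.20, it is about 5.8% / 7.1% / 9.3%. Holm's procedure takes each p-value as valid, so it does not repair an understated SE.

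**The case against.** The strongest case against is that all the harm rests on an ICC the documents do not supply, and that the design gives reasons to expect a small one: manualised content, one clinician for every group, and computer exercises worked individually. At ICC 0 nothing is wrong; at 0.05 coverage is 93.5%, a small loss. Every paired t-test carries an independence assumption, the estimate is unbiased either way, and the plan disclaims definitive efficacy conclusions. All of this stands, and it sets the weight of the point. It does not remove it: a single clinician rules out differences between therapists but not peer or calendar effects, and Aim 2 still tests two primary outcomes at 5%.

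A reader might infer more than the documents support in three places.

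- **That the mixed model is shown to ignore groups.** Section 3.G gives the correlation between time points but does not list random effects. What can be said is that no group term is stated. The model is also exploratory.
- **That the 90% power is wrong.** It is right under independence, and the planned test's rejection rate at 3.2 points falls only to 87% even at ICC 0.20.
- **That the family-wise error is as high as 13.5%.** That figure needs a two-outcome family, ICC 0.20, and as much clustering in a cognitive task as in a mood rating. The documents establish none of these.

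**Conclusion.** The point holds in conditional form. The plan treats Veterans in six groups of six and analyses Aim 2 as though their changes were independent, without saying so. With 22 completers, an ICC of 0.05 to 0.20 means an SE understated by a factor of 1.07 to 1.24 and a 5% test that runs at about 6.5% to 11.5%. The ICC range, the even spread of completers and normal changes are assumptions; the upper end should not be read as the expected case.

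The weight is low, a matter for the sponsor to consider. It would be too strong to conclude that the primary test must be replaced or that a positive result would be invalid: this is a single-arm pilot, and the documents neither state nor imply a material ICC. Nor do the documents say whether the later RCT will treat in groups, so any effect on its sample size is conditional on that.

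**What to change.** Keep the paired t-test as primary and make two additions to section 3.G.

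1. State that the 5% alpha and 90% power assume independent changes among Veterans in the same therapy group.
2. Pre-specify one sensitivity analysis in study completers for MADRS and IGT, to be run whatever the primary result: the mean and 95% CI of the group mean changes, using t with number of groups minus 1 df (5 if every group has a completer), reported beside the primary CI.

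Group membership is known by design, so no new data are needed. With completers spread 4, 4, 4, 4, 3, 3 this test holds about 5% type I error at every ICC examined. Its cost is precision:

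- Power at 3.2 points (5% level) is about 78% / 73% / 69% / 61% at ICC 0 / 0.05 / 0.10 / 0.20. With uneven dropout (6, 5, 4, 3, 2, 2 completers) it is about 72% / 68% / 64% / 58%.
- The mean CI width is about 4.6 / 4.9 / 5.1 / 5.6 MADRS points, against 3.8 for the primary.
- Veterans in depleted groups count for more, so the quantity estimated differs somewhat from the primary one.

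A non-significant sensitivity result is therefore weak evidence against the primary, and the plan should say so.

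Do not prescribe a version that pools group means over imputed datasets by Rubin's rules. With 14 of 36 changes imputed without covariates and 5 complete-data df, simulation leaves about 2 to 3 df, type I error at or below about 0.5%, and power of about 16% to 34%. Predictive covariates would soften this, but the completer version is clearer and matches the population named for the paired t-test.

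Any ICC estimated from the pilot should be descriptive only: at a true value of 0.05 with 22 completers, the central 95% of estimates runs from about −0.29 to 0.46. If the later RCT treats in groups, it should be sized over a range of assumed ICCs.

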1.C. Telehealth During the Time of COVID-19. Given mandated social-distancing policies to prevent the spread of COVID-19 and ongoing concern regarding virus transmission months after the initial submission of this project, the bi-weekly CR+Bridging intervention will be conducted via telehealth. Under normative circumstances, the CR+Bridging intervention would be conducted in person. However, with consistent and ongoing support and guidance from [name] and [name], those aspects have been adapted for telehealth, an additional novel feature of the current study. This format not only serves to protect the health of the patients and increase social connections for a certain population of individuals shown to benefit from maximizing support from a range of social ties,²⁸ it also aims to increase patient engagement and decrease no-show rates. However, the assessments (see **Table 3.D**) at the various timepoints: pre- (**Baseline**), post-intervention (**Week 10**) and follow-up (**Week 20**) will be administered in person and abiding by strict COVID-19 safety precautions (e.g., health screening on day prior and day-of visit, temperature check, socially distanced throughout visit, sanitization of all testing materials and furniture before, during, and after each visit).

2. Preliminary Work

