disabling conditions to function more fully in society” and (2) may provide new targets for suicide prevention/intervention. With supervision and support from [name] and [name], each session follows the CR+Bridging format and is tailored to address the specific cognitive control and decision-making/problem solving deficits linked to suicidal behavior in this patient population. The widely used computerized exercises utilized during the initial portion of each session are modeled after those proven to be effective at improving cognitive control and decision-making/problem-solving skills in psychiatric populations with weakness in those areas.^{41, 42} The Bridging session that immediately follows each cognitive training session involves consistent practice of learned cognitive control and problem-solving strategies, ultimately enabling patients to exert better control over emotion regulation processes in stressful situations. Each session involves the following: (1) Use of password to enter telehealth platform; (2) Verify confidentiality/privacy with all patients; (3) Check-in regarding status of each patient’s technology and print log/journal; (4) Check-in with patients regarding their mood; (5) Share screens depicting their computer-based cognitive training and initiate use of exercises; (6) Break; (7) Quit all members’ sharing of screens and initiate Bridging session to promote transfer of skills learned in context of computer-based training to a broader set of real-world scenarios; (8) Complete log/journal and list tasks for next session. See **Table 3.A** for brief summary of content for each active learning plan/session. See **Appendix 4** for Individual Session Log and examples of Bridging Group content.

Table 3.A. Bridging Session Content.

Week/Session #	Targeted Cognitive Skills	Transfer to Daily Functioning Skills in Bridging Session

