3.D. Clinical, Cognitive, Social, and Adaptive Functioning Assessments and Schedule. Patients referred from [name] current VA Merit study will already have been screened/diagnosed using the Structured Clinical Interview for DSM-5 Disorders (SCID),⁴⁶ Structured Interview for DSM-5 Personality Disorders (SCID-PD),⁴⁷ and the C-SSRS.⁴⁴ We use the SCID-PD given our interest and prior work in borderline personality disorder (BPD), and because many high-risk Veterans meet criteria for BPD, e.g., see³⁰. These three assessments will be reviewed for any interested participants once they have consented for the current study. Additionally, the Ruminative Response Scale⁴³ will be administered during the screening process to determine whether they meet the study inclusion criteria for poor cognitive control problems (see **3.C. Inclusion**). Participants will be enrolled in the intervention and undergo assessments (**Table 3.D**) at the various timepoints: pre- (**Baseline**), post-intervention (**Week 10**) and follow-up (**Week 20**) to be administered in person and abiding by strict COVID-19 safety precautions (e.g., health screening on day prior and day-of visit, temperature check, socially distanced throughout visit, sanitization of all testing materials and furniture before, during, and after each visit).

Following baseline assessments, Veterans will participate in the CR+Bridging sessions (2x/week for 10 weeks; i.e. 20 sessions) via telehealth with a clinical neuropsychologist ([name]/Co-I, who will administer all treatment sessions and train MIRECC Advanced Psychology Fellows on the intervention). [name] (Co-I) will conduct all clinical assessments blind to the patients’ progress in the CR+Bridging sessions.

Table 3.D. Clinical, Cognitive, Social, Adaptive Functioning Assessment Schedule. Primary outcome variables are **bold** font.

Assessment:	Domain	Baseline (Pre-Tx)	Week 10 (Post-Tx)	Week 20 (Follow-Up)
Demographics	Demographics	X		
Structured Clinical Interview for DSM-5 Disorders ⁴⁶	Diagnostic	X		
Structured Clinical Interview for DSM-5 Personality Disorders ⁴⁷	Diagnostic	X		
Columbia-Suicide Severity Rating Scale (C-SSRS) ⁴⁴	Diagnostic	X	X	X
Ruminative Response Scale ⁴³	Rumination	X	X	X
Cognitive Remediation Fidelity Scale ¹⁰	Fidelity		X	
Patient and Therapist Satisfaction Questionnaire (see Appendix 5)	Feasibility/Acceptability		X	X
Intrinsic Motivation Inventory ⁴⁸	Motivation	X	X	
Revised Helping Alliance Questionnaire ⁴⁹	Therapeutic Alliance		X	

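### Week 10 and Week 20 assessments are in person with no remote fallback, so a missed site visit loses a MADRS and a C-SSRS that the assessor could probably collect by telehealth

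*Combined protocol and SAP*

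**What the plan says.** Treatment and assessment use different modes. Section 1.C states that "the bi-weekly CR+Bridging intervention will be conducted via telehealth", and then, as an explicit contrast, that the Table 3.D assessments at all three time points "will be administered in person and abiding by strict COVID-19 safety precautions". Section 3.D repeats this: the assessments are "to be administered in person and abiding by strict COVID-19 safety precautions (e.g., health screening on day prior and day-of visit". Table 3.D schedules both the MADRS and the C-SSRS at Baseline, Week 10 and Week 20.

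One reason given for telehealth treatment is attendance. Section 1.C says of the format that "it also aims to increase patient engagement and decrease no-show rates", and section 3.F says of the intervention study that "it involves telehealth, making it more appealing to participants and less prone to high no-show rates". Section 3.A lists what happens on the platform at each session, including password entry, a privacy check, screen sharing and "Check-in with patients regarding their mood".

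Section 3.G refers to the "clinician-administered MADRS" and names the MADRS and the Iowa Gambling Task (IGT) as primary outcomes. Completers are compared between Baseline and Week 10 by paired t-test. Missing data are assumed missing at random and multiply imputed. Section 3.D has one co-investigator do all clinical assessments, blind to progress in treatment.

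**The concern.** The plan has a working video link to each participant and a single blinded assessor, yet it does not say what happens when a Week 10 or Week 20 site visit fails. As written, a Veteran who has been attending sessions by video and misses the Week 10 visit contributes no observed MADRS change and no scheduled C-SSRS rating.

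Two things are at stake. The first is the primary depression comparison. A missing value has to be either left out of a completer analysis or imputed under an assumption that cannot be checked. If those who miss the visit differ in depression from those who attend, the completer estimate is biased, and imputation may not repair it. The second is the follow-up suicide rating, in a sample selected for an attempt within the past year and current ideation.

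Precision also has some value here, because section 3.G intends the pilot data to inform the power of a later confirmatory trial.

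**Working it through.** **Inputs, all from section 3.G.** Mean paired difference 3.2, SD of differences 4.35, two-sided alpha 0.05, 22 completers, 36 enrolled, up to 40% attrition.

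**Step 1: reproduce the plan's figure.** The standardised difference is 3.2/4.35 = 0.736. For n pairs, the paired t-test has n − 1 degrees of freedom and noncentrality 0.736 × √n. At n = 22 the noncentrality is 0.7356 × 4.690 = 3.45 and the critical value is t(0.975, 21) = 2.080. The noncentral t distribution gives power of 90.8%. The stated 90% is reproduced.

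**Step 2: slack at the attrition limit.** 36 × 0.60 = 21.6, which the plan rounds to 22. With 21 pairs power is 89.4%, so 22 is the smallest number that reaches 90%. At its own attrition limit the plan meets its target with nothing spare.

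**Step 3: what recovered pairs would be worth.** The plan allows 36 − 22 = 14 losses from all causes. It does not say how many would be missed visits by Veterans still in the study, so the recovered numbers below are assumptions. Half-width = t(0.975, n − 1) × 4.35/√n.

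| Recovered (assumed) | Pairs | t(0.975, n − 1) | 4.35/√n | 95% CI half-width | Power |
|---|---|---|---|---|---|
| 0 (plan) | 22 | 2.080 | 0.927 | 1.93 | 91% |
| 3 | 25 | 2.064 | 0.870 | 1.80 | 94% |
| 5 | 27 | 2.056 | 0.837 | 1.72 | 96% |
| 7 | 29 | 2.048 | 0.808 | 1.65 | 97% |

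The SD is held at 4.35 throughout. Mixing video and in-person ratings could raise it somewhat, which would reduce the gain.

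**Step 4: which measures a fallback could cover.** The MADRS is described as clinician-administered, and the C-SSRS is a rating interview. That both could be done on the platform is a reasonable inference from the session features in section 3.A, but the document neither states nor tests it. The IGT, Tower of Hanoi, Stroop, Go/No-Go and Naming tests are performance tests and would stay on site. The document does not give the format of most remaining scales, so each needs checking before it is called remote-ready.

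**The case against.** The strongest reply is that in-person assessment is a deliberate choice. Section 1.C sets it against telehealth treatment and adds safety precautions, and a single mode keeps each Baseline and Week 10 pair comparable. This stands as a reason to keep in person as the default. It does not justify having no value at all when the visit fails, because a video rating with its mode recorded can be set aside in a sensitivity analysis.

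Several stronger readings are tempting, and the documents do not support them:

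- A reader might infer that the plan itself says site visits produce more no-shows. Its no-show statements concern the telehealth intervention of 20 sessions, not two follow-up visits.
- A reader might infer that the health screens cancel visits. Section 3.D does not say what follows a failed screen, nor that a visit cannot be rescheduled.
- A reader might infer that many participants cannot or will not travel. Enrolled Veterans have already attended Baseline in person and are in psychotherapy at the same medical centre, so the number recovered may be small.
- A reader might infer that missed visits leave suicide risk unobserved. Participants are in ongoing psychotherapy, have a mood check-in at each session, and are reported on to their psychiatric team. What is lost is the scheduled research rating, which those contacts do not replace.

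It is also fair to say that this is an open pilot that disclaims conclusions on efficacy, that it budgets for 40% attrition and specifies imputation, and that section 3.B points to a Human Subjects section and an appendix that are not in the document reviewed and might contain a missed-visit procedure.

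**Conclusion.** The point holds as a cheap improvement, not as an error. In the document reviewed, all follow-up assessment is in person and no remote fallback is given. Adding one would replace some missing MADRS and C-SSRS values with observed ones.

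The size cannot be derived from the documents. Under the assumption of 3 to 7 recovered pairs, power for a 3.2-point change goes from 91% to between 94% and 97%, and the half-width narrows by 0.13 to 0.28 points (1.93 − 1.80 and 1.93 − 1.65). The gain in precision is modest. Less reliance on the missing-at-random assumption may matter more, but nothing in the documents shows that missed visits would be related to severity.

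A reader might infer that the sample size is inadequate. It is not shown to be: the stated power is right, and the 40% allowance may already include missed visits. Nor would the fallback rescue both primary outcomes. A Veteran who misses the site visit would still lack the IGT.

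**What to change.** First state whether a missed-visit procedure exists elsewhere. If it does not, amend sections 1.C, 3.D and 3.G as follows:

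- Keep in person as the default at every time point.
- When a Week 10 or Week 20 site visit is missed and cannot be rescheduled near its due date, have the same blinded assessor complete the MADRS and C-SSRS by telehealth. Hold this apart from the treatment sessions so that blinding is kept.
- Collect remotely those questionnaires whose format allows it.
- Keep the IGT and the other performance tests in person, and report them as missing when the visit is missed.
- Say in section 3.G that a Veteran with a remote Week 10 MADRS counts in the MADRS comparison. The section does not define a completer, so such a person could otherwise be left out.
- Record the mode of each assessment, and repeat the MADRS comparison with in-person pairs only as a sensitivity analysis.

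The cost is a short amendment, confirmation that the assessor can use the platform, and some pairs with an in-person Baseline and a video Week 10. No visit that would have taken place in person is affected.
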